### **C.11. Intervention Component – Booster Level Phone Calls**

Patients whose systolic blood pressure comes under control at 6 or 12 months will be switched to booster level resource intensity LPN phone calls (based on procedures described in section C.9.b). The calls will occur every two months instead of monthly and be conducted by a LPN instead of an RN. The number of contacts will depend on the point in the study when LPN calls begin and changes made during titrations. Unlike the RN and pharmacist, the LPN will not receive training in motivational interviewing. Further, specific behavioral modules that are activated will not be tailored to the patient and the LPN will not ask for information about any home BP measurements. The goal is to identify stable patients and reduce the resources they use to minimize cost of our intervention.

LPNs [known as licensed vocational nurses (LVNs) in California and Texas] differ from RNs in several important dimensions. While both are nurses, LPNs focus on providing specified services under the direction of another licensed clinician, often a RN. While RNs can assess patients and develop plans for nursing care, LPNs cannot independently assess and take action in relation to patient care. As we propose for this study, LPNs can complete assigned patient care tasks, observe patients, and report observations to other clinicians. Further, RNs have training in areas such as educating patients about health issues. As a result of their greater responsibilities, RNs are paid significantly more than LPNs.

Because this is a pragmatic clinical trial, it is expected that some patients may not be able to be contacted or miss some portion of the scheduled telephone calls or other contacts with study personnel.

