### D.2. Analysis of Primary Hypothesis

**Veterans randomized to the titrated disease management intervention arm will have greater improvement in mean systolic blood pressure over the 18 months of follow-up than veterans randomized to the control arm.**

The purpose of the Primary Aim is to examine the impact of titrated disease management on mean systolic blood pressure over 18 months, and the trial is powered to detect a 5 mmHg difference between the two treatment arms (see sample size section D.3 below). As described above, blood pressure will be measured on all patients at baseline, 6, 12, and 18 months of follow up. A general linear model will be used to estimate changes in mean systolic blood pressure over time and test the primary hypothesis. Linear models are a flexible and powerful analytic tool for repeated continuous measures, such as systolic blood pressure.

The predictors in the model will include a time effect and the intervention-by-time interaction. We will use the results from our exploratory graphical methods as well as AIC and BIC fit indices to select the most appropriate way to model time for the two treatment groups over the 18 month follow up. In previous studies, we have generally observed a quadratic trend over time in the intervention group, where patients in the intervention group improve the first half of the study and sustain improvement for the remainder of the study. Other possibilities include a linear trend or categorical (i.e., dummy coded) time. The stratification

variables of baseline level of blood pressure control and diabetes status will also be included. A model with categorical time is shown below in equation (1):

$$SBP = \beta_0 + 6month*\beta_1 + 12month*\beta_2 + 18month*\beta_3 + 6month*IntArm*\beta_4 + 12month*IntArm*\beta_5 + 18month*IntArm*\beta_6 + baselineBPcontrol*\beta_7 + diabetes*\beta_8 + \epsilon$$

We will use our exploratory descriptive and graphical methods for variability and correlation as well as AIC and BIC fit indices to determine an appropriate covariance structure for to take into account the within-patient correlation between repeated measures over time. In previous studies, we have found that either a random intercept-slope (i.e., growth curve model) specification for the random effects or an unstructured covariance matrix has been most appropriate.

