We will estimate the parameters in the model using the SAS procedure MIXED and contrasts will be written in the context of this model to test the treatment difference at month 18. Furthermore, if the intervention-by-time terms in the model are significant, this provides evidence that the difference in systolic blood pressure between the two treatment groups over the 18 months of follow up is not constant, that is, it is time-dependent. This is an omnibus test contrasting the two treatment groups at the 6, 12, and 18 month time points. If this interaction test is significant and if it represents a qualitative, rather than a quantitative effect, this will provide insight into the different time-dependent patterns for each intervention group. As a summary, model estimated means and confidence intervals of systolic blood pressure will be generated at each time point for both treatment groups. Additionally, simultaneous confidence intervals on the treatment group differences will be generated for each time point.

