### D.3. Sample Size and Power Considerations

The sample size estimate is based on the primary hypothesis: veterans randomized to titrated disease management will have lower mean systolic blood pressure at 18 months than veterans randomized to bi-monthly LPN-delivered telephone calls. A 5 mmHg improvement at 18 months will be the definition of a minimally clinically significant difference. This represents the differential between the two treatment groups at 18 month; therefore, the power and sample size considerations, apply even if the control group also improves over the 18 month study period (i.e., "placebo" effect). For example, if the control group improves from 145 mmHg to 142 mmHg, we will have adequate power to detect a 5 mmHg differential improvement – the intervention group improves from 145 to 137 mmHg.

Sample size calculations are based on ANCOVA methods as presented in Borm et al. We used data from previous studies to estimate quantities needed for the sample size calculation. We anticipate a common mean systolic blood pressure of 145 mmHg, a standard deviation of 17.5 mmHg in both treatment groups at baseline, and a correlation between time points equal to 0.4. Finally, based on previous studies, we estimate a 15% attrition rate by 18 months. From the calculation, we determined that **we will need to enroll until we randomize 400 patients (200 randomized in each group)** to detect a 5mmHg difference at 18 months with 80% power and a type-I error of 5%. Based on our prior recruitment experience, we consider this to be feasible given the 18 months timeframe (on average 6-7 patients per week), the potential for over 3,800 eligible individuals in Durham and a total of ~7,900 in all Durham affiliated clinics, and the requested resources. We note that these calculations do not reflect that stratification variables will be included in the final analysis model described above. Stratification variables are expected to account for variability in the outcome. The projected sample size analysis is therefore conservative, and we anticipate that there will be greater power to detect between-group differences with this study size.

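### D.2 reads a significant intervention-by-time test as a non-constant arm difference, but under equation (1) it is a global test of any difference and would reject in about 80–93% of trials with a steady 5 mmHg effect

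*Protocol*

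**What the plan says.** Protocol D.2 specifies the repeated-measures model for SBP: "The predictors in the model will include a time effect and the intervention-by-time interaction". Equation (1), the categorical-time version, contains the intervention arm only through its products with the 6-, 12- and 18-month indicators (β4, β5, β6). The time form is to be chosen by graphics, AIC and BIC. A quadratic form is mentioned first, and then "Other possibilities include a linear trend or categorical (i.e., dummy coded) time".

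The primary test is a contrast at month 18. D.2 adds that significant intervention-by-time terms are evidence that "the difference in systolic blood pressure between the two treatment groups over the 18 months of follow up is not constant". The next sentence describes the same test differently: "This is an omnibus test contrasting the two treatment groups at the 6, 12, and 18 month time points". A significant result, if it also represents a qualitative rather than a quantitative effect, is then to be used to describe the time pattern in each arm. D.2 also promises that "model estimated means and confidence intervals of systolic blood pressure will be generated at each time point for both treatment groups", with simultaneous intervals for the differences.

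**The concern.** A significant arm-by-time interaction shows a changing difference only when the model also has an arm main effect to carry the constant part. Equation (1) has none, so the two D.2 sentences give one test two meanings, and only the second fits the model. A trial with a perfectly steady effect would usually be reported as having a time-dependent one.

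Whether the effect lasts is a natural question in this design. Under C.11, "Patients whose systolic blood pressure comes under control at 6 or 12 months will be switched to booster level resource intensity LPN phone calls", and these are the calls that the control arm receives throughout. A reader will want to know whether the benefit holds after that step-down. The test as interpreted cannot separate a held effect from a waning one.

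**Working it through.** **Inputs.** From D.3: SD 17.5 mmHg, "a correlation between time points equal to 0.4", 5 mmHg difference, type I error 5% (taken as two-sided), 200 per arm, 15% attrition, hence 200 × 0.85 = 170 per arm. Assumed here: the same SD at every visit, compound symmetry, and complete data on the 170. A follow-up correlation of 0.5–0.7, with the baseline correlation kept at 0.4, is a sensitivity assumption.

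**The plan's own figure.** The ANCOVA SD is 17.5 × √(1 − 0.4²) = 16.04. This needs 162 per arm, or 162/0.85 → 191 per arm, 382 in total. With 170 completers per arm, power at month 18 is 82%. The stated 400 for 80% power is therefore consistent, with a small margin.

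**What the coefficients mean.** In equation (1) both arms share the baseline mean β0. The modelled arm difference is 0 at baseline and β4, β5, β6 at 6, 12 and 18 months.
- D.2 interaction test: β4 = β5 = β6 = 0 (3 df), meaning no difference at any visit.
- Constancy over follow-up: β4 = β5 = β6 (2 df), meaning the same difference at each visit.

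**Covariance of the estimated differences.** V = (2/170) × Σ, where Σ is the follow-up covariance given baseline.
- Diagonal: 306.25 × (1 − 0.16) = 257.25.
- Off-diagonal: 306.25 × (0.4 − 0.16) = 73.5.
- SE per visit: √(2 × 257.25/170) = 1.74.

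For differences with mean m and sum of squared deviations SS about m, the noncentralities are:
- 2-df: 85 × SS/(257.25 − 73.5) = 85 × SS/183.75.
- 3-df: 85 × 3m²/(257.25 + 2 × 73.5) + the 2-df value = 255m²/404.25 + the 2-df value.

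| True difference at 6/12/18 months | 3-df noncentrality | 3-df significant | 2-df noncentrality | 2-df significant |
|---|---|---|---|---|
| 5/5/5 (flat) | 255 × 25/404.25 = 15.77 | 93% | 0 | 5% |
| 2.5/5/5 (builds, then holds) | 10.95 + 1.93 = 12.88 | 87% | 85 × 4.167/183.75 = 1.93 | 22% |
| 5/5/2 (wanes) | 10.09 + 2.78 = 12.87 | 87% | 85 × 6/183.75 = 2.78 | 30% |

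The second row is one numerical version of the pattern that D.2 expects, where "patients in the intervention group improve the first half of the study and sustain improvement for the remainder of the study".

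**Sensitivity for the flat difference.** At follow-up correlations 0.5, 0.6 and 0.7 the 3-df test is significant in 89%, 84% and 80%. The 3-df test is significant while the 2-df test is not in 88% at correlation 0.4, and in 84%, 79% and 75% at 0.5, 0.6 and 0.7 (400,000 draws). Simulated trials of the four-visit model with an estimated unstructured covariance gave 93–94% for the 3-df test and 4–6% for the 2-df test at correlation 0.4.

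**If linear or quadratic time is selected.** With no arm main effect the difference is a·t, or a·t + b·t².
- Equality at 6 and 12 months needs 6a + 36b = 12a + 144b, so a = −18b.
- Equality at 12 and 18 months needs 12a + 144b = 18a + 324b, so a = −30b.
- Both hold only when a = b = 0, so a steady non-zero difference is outside the model.

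A true 5/5/5 is fitted on average (generalized least squares, correlation 0.4) as 1.8/3.7/5.5 under linear time, where month 18 is always three times month 6, and as 4.1/5.7/4.6 under quadratic time.

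**The case against.** - **Baseline may count.** If follow-up includes month 0, where the difference is zero, any non-zero coefficient does mean that the difference changed. This makes the sentence literally true but empty: not constant then means only that an effect exists. The next sentence of D.2 also names only 6, 12 and 18 months.
- **D.2 describes the test correctly one sentence later.** True, and this is why the fix is small. The inferential rule that precedes it is still wrong for months 6–18.
- **The follow-on step also requires a qualitative effect.** Flat and waning effects do not reverse sign, so most such trials would not meet that condition. This stands. The 88% counts trials labelled time-dependent while the equality contrast is not significant, not trials in which the later step goes wrong.
- **Other output would show the pattern.** D.1 plans mean trajectory plots that do not depend on the time form, and the quadratic fit to 5/5/5 is off by at most 0.9 mmHg against an SE of 1.74. Both points stand as mitigation. The per-visit estimates in D.2 are model-based, however, and are trustworthy for this purpose only with categorical time.
- **Linear time may not be chosen.** In 1,500 simulated trials with a flat 5 mmHg effect, linear time was selected in 0.5% (AIC) or 18% (BIC) when the control arm fell 3 mmHg from month 6, and in 18% or 75% when the control arm stayed flat. The linear distortion is conditional, but not remote under BIC.
- **No planned conclusion changes.** Correct: no hypothesis in A.1 concerns constancy. This sets the severity and does not remove the error.

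**Conclusion.** The concern holds and is minor. Under equation (1) the intervention-by-time test is a global test of any arm difference at 6, 12 or 18 months, so the stated reading of a significant result is wrong for the follow-up period. At the protocol's correlation of 0.4 it is significant in 87–93% of trials whether the effect is flat, builds or wanes, in the patterns worked above. The 93% for a flat effect uses the only correlation that the protocol gives; the 80% end rests on an assumed 0.7 between follow-up visits. The figures assume equal SDs and 170 complete patients per arm. Adding partial data from dropouts (5% lost per interval) raises the flat-effect range to about 84–95%. The month-18 contrast, its power and the sample size are untouched.

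**What to change.** In D.2:
1. Describe the joint test of the intervention-by-time terms as a supportive global test of any treatment difference, and delete the inference that significance shows a non-constant difference.
2. Assess change across 6, 12 and 18 months with the 2-df contrast β4 = β5 = β6 from the categorical-time model, whichever time form is selected for the primary analysis.
3. Apply the qualitative-versus-quantitative step only after that contrast.
4. Report the contrast with the categorical-time differences at each visit and their simultaneous intervals.
5. State that a non-significant contrast is not evidence of constancy. At correlation 0.4 its power is about 30% against 5/5/2 and 22% against 2.5/5/5. At an assumed follow-up correlation of 0.7 it is still only about 40–55%.

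The cost is one contrast statement from a categorical-time fit and a few sentences of wording. Data collection, sample size and the primary test do not change.

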### D.3. Sample Size and Power Considerations

The sample size estimate is based on the primary hypothesis: veterans randomized to titrated disease management will have lower mean systolic blood pressure at 18 months than veterans randomized to bi-monthly LPN-delivered telephone calls. A 5 mmHg improvement at 18 months will be the definition of a minimally clinically significant difference. This represents the differential between the two treatment groups at 18 month; therefore, the power and sample size considerations, apply even if the control group also improves over the 18 month study period (i.e., "placebo" effect). For example, if the control group improves from 145 mmHg to 142 mmHg, we will have adequate power to detect a 5 mmHg differential improvement – the intervention group improves from 145 to 137 mmHg.

Sample size calculations are based on ANCOVA methods as presented in Borm et al. We used data from previous studies to estimate quantities needed for the sample size calculation. We anticipate a common mean systolic blood pressure of 145 mmHg, a standard deviation of 17.5 mmHg in both treatment groups at baseline, and a correlation between time points equal to 0.4. Finally, based on previous studies, we estimate a 15% attrition rate by 18 months. From the calculation, we determined that **we will need to enroll until we randomize 400 patients (200 randomized in each group)** to detect a 5mmHg difference at 18 months with 80% power and a type-I error of 5%. Based on our prior recruitment experience, we consider this to be feasible given the 18 months timeframe (on average 6-7 patients per week), the potential for over 3,800 eligible individuals in Durham and a total of ~7,900 in all Durham affiliated clinics, and the requested resources. We note that these calculations do not reflect that stratification variables will be included in the final analysis model described above. Stratification variables are expected to account for variability in the outcome. The projected sample size analysis is therefore conservative, and we anticipate that there will be greater power to detect between-group differences with this study size.

### D.4. Analysis of Secondary Hypothesis – Systolic Blood Pressure Control

Systolic BP control (< 140 mmHg for patients without diabetes and < 130 mmHg for patients with diabetes (different definitions may be modeled as part of sensitivity analyses) will be determined at the 6, 12, and 18 month study visits based on study BP measurements (process described in section C.18). We plan to model the probability of having controlled systolic BP over time and test this secondary hypothesis using generalized linear mixed models as applied in PROC GLIMMIX with adaptive quadrature. The mixed model will include time, the treatment by time interaction (with time dummy coded), and the stratification variables. To account

for the within-patient correlation over time, we have found that either a random intercept-slope (i.e., growth curve model) specification for the random effects or an unstructured covariance matrix is most appropriate.

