## **C.6. Randomization**

1. Once a patient has consented and completed the measurement battery, the patient will be randomized to one of the 2 study arms.

2. We will stratify randomization by diabetes status (because of differing hypertension treatment goals) and baseline SBP [SBP Low Strata = < 150mmHg and High Strata = SBP ≥ 150 mmHg for non-diabetic patients and Low Strata = SBP < 140mmHg and High Strata = SBP ≥ 140 mmHg for diabetic patients]. Diabetes is defined as having both: ICD 250.xx on ≥ 2 outpatient encounters during the prior year and prescription for oral hypoglycemic medication (e.g., sulfonylurea, metformin, thiazolidinedione, secretagogues, acarbose) and/or insulin during the past year. Data for the diabetes status variables will come from the data pull for evaluating inclusion/exclusion criteria and SBP is an average of study assessed readings at baseline.

3. Randomization will occur within the study computerized database. As a backup, randomization assignments by strata may be placed in sealed, consecutively numbered envelopes by a masters-level statistician before patient enrollment begins. Other similar systems for randomization, developed in consultation with study statisticians, may also be used as backup.

4. We will use blocked randomization; to prevent contamination, research assistants will be blinded to block size.

5. Patients will be told the arm to which they are assigned by the RA (or other appropriate study staff member) at the enrollment study visit. If the patient must leave the study appointment after informed consent and HIPAA Authorization have been obtained, but before randomization, the arm assignment will be revealed to the patient over the phone.

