#### **D.7. Missing Data**

Because the main predictors of interest, treatment group and demographics, are collected at baseline, we do not anticipate much missing data in these variables. There may be missing values in the outcome measures due to drop-out, a missed interim assessment, or item non-response. Given a thorough understanding of the missing data mechanism, it is possible to use all of the available information in analysis, rather than using only subjects with completely observed information. Our main analysis technique, general linear models via maximum likelihood estimation, implicitly accommodates missing data when the response is Missing At Random (MAR); that is, when missing data is due either to treatment, to prior outcome, or to other baseline covariates included in the model. Therefore, inferences will be valid even if we have differential dropout by treatment group. Depending on the type and scope of missing data, we will also explore multiple imputation as a strategy to use in conjunction with our primary analytic tools. Finally, following recent guidelines published by the National Research Council's Panel on Handling Missing Data in Clinical Trials, we will conduct sensitivity analyses with sets of pattern-mixture models to examine the degree to which our primary analyses and inferences are dependent upon missing data assumptions.

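### The model for SBP control (H2) uses baseline SBP only as a two-level stratum; adding the continuous value already collected would recover a little information at almost no cost

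*Protocol*

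**What the plan says.** D.4 specifies a generalised linear mixed model for SBP control. Its fixed effects are listed in full: "The mixed model will include time, the treatment by time interaction (with time dummy coded), and the stratification variables". The responses are the follow-up visits only, since control "will be determined at the 6, 12, and 18 month study visits based on study BP measurements".

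C.6 says what the stratification variables are: "We will stratify randomization by diabetes status (because of differing hypertension treatment goals) and baseline SBP". The SBP factor has two levels, cut at 150 mmHg without diabetes and 140 mmHg with diabetes. The same section says that the underlying "SBP is an average of study assessed readings at baseline", so the continuous value exists for each randomised patient. D.2 confirms that "blood pressure will be measured on all patients at baseline, 6, 12, and 18 months of follow up".

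The primary model in D.2 treats baseline differently. Equation (1) has dummies for months 6, 12 and 18 and no arm main effect, so baseline is the reference visit and the measured baseline SBP is one of the responses. The sample size in D.3 also relies on the continuous baseline, through an ANCOVA formula with correlation 0.4.

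On missing data, D.7 states: "Our main analysis technique, general linear models via maximum likelihood estimation, implicitly accommodates missing data" under missing at random, which it explains as holding "when missing data is due either to treatment, to prior outcome, or to other baseline covariates included in the model". It adds that "we will also explore multiple imputation as a strategy to use in conjunction with our primary analytic tools", and it plans pattern-mixture sensitivity analyses for the primary analyses.

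**The concern.** How far above the control threshold a patient starts is a natural predictor of reaching it. The two-level stratum keeps only part of that. In the high stratum, which has no upper limit, a non-diabetic patient at 152 mmHg and one at 185 mmHg are treated alike. Baseline control status cannot fill the gap, because the trial enrols patients whose SBP is uncontrolled (C.1, C.23).

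Two things could be at stake. The first is precision for a secondary hypothesis that has no power calculation of its own. The second is missing data. A patient lost before month 6 contributes no response to the D.4 model, so dropout related to that patient's SBP can be handled only through the covariates, and within a stratum the SBP value is not among them. In the primary model the same patient still contributes the baseline reading.

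**Working it through.** **Inputs from the protocol.** SD 17.5 mmHg, correlation 0.4 between time points, difference 5 mmHg at month 18, 80% power, 5% type I error, 15% attrition, 200 per arm, and example means falling from 145 to 142 (control) and 137 (intervention), all from D.3. About 130 of 200 intervention patients are expected at the medium level at baseline (Table 2), and C.9.a uses the same SBP cuts as the stratum, so about 65% are in the low stratum. Control cut-offs are 140 and 130 mmHg (D.4).

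**The plan's own figure.** No sample size or power is stated for H2. For H1, with a two-sided test (assumed):

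- Unadjusted: 2 × (1.960 + 0.842)² × 17.5² / 5² = 192.3 per arm.
- ANCOVA factor: 192.3 × (1 − 0.4²) = 161.5, so 162 per arm.
- Attrition: 162 / 0.85 = 190.6, so 191 per arm, 382 in total.
- At 200 × 0.85 = 170 completers per arm, power is 82.0%.

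The stated 400 is a round-up of 382. The D.3 inputs can be carried forward.

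**What the split keeps, on the continuous scale.** For a normal variable cut so that 65% lie below, the correlation between the value and its indicator is φ(0.385) / √(0.65 × 0.35) = 0.370 / 0.477 = 0.777.

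- Follow-up variance explained by the continuous value: 0.4² = 16%.
- Explained by the stratum: 0.777² × 16% = 0.603 × 16%, about 9.6%.
- Residual variance ratio: 0.84 / 0.904 = 0.93, about 7%.

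Dichotomising the outcome shrinks this gain, so the binary model has to be simulated.

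**Simulation of the D.4 model.** 400 patients; random-intercept logistic model with time, treatment by time, diabetes and SBP stratum, with and without continuous baseline SBP; test of the month-18 treatment term. Assumed, because the protocol does not give them: 40% with diabetes, diabetic mean 10 mmHg lower, exchangeable correlation, 5 mmHg effect at every visit, monotone dropout totalling about 15%. Baseline SBP was either untruncated or truncated at the control cut; the truncated case is closer to C.23. Information gain is the squared ratio of mean z statistics.

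| Baseline SBP | Replicates | Information gain | Power, stratum only | Power, with baseline SBP |
|---|---|---|---|---|
| Untruncated | 686 | 3.1% | 59.3% | 59.8% |
| Truncated | 487 | 1.5% | 60.8% | 59.8% |

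The simulation standard error of one power figure is about √(0.6 × 0.4 / 686) = 1.9 points, or 2.2 points with 487 replicates, so neither change is detectable.

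**Month-18 logistic model** (2,500 replicates per setting, dropout at random, same correlation). Gains run from about 2% to 4%. Examples: untruncated, 30% with diabetes, 58.1% to 59.2%; truncated, 40% with diabetes, 60.6% to 61.8%. The largest reported change is 58.0% to 61.0%.

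**Dropout depending on baseline SBP** (logistic slope 0.8 per SD, assumed). When the dependence was the same in both arms, the month-18 model showed no detectable bias: with truncated baseline, a risk difference of 11.7 points from the stratum-only model against 11.7 in the full data. When the dependence ran in opposite directions by arm, the mixed model gave:

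| Baseline SBP | Full data | Stratum only | With baseline SBP |
|---|---|---|---|
| Untruncated | 11.0 points | 10.0 points | 11.1 points |
| Truncated | 11.6 points | 10.8 points | 11.3 points |

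**The case against.** The strongest reply is that nothing in D.4 is wrong. Adjusting for the stratification factors is a conventional model that respects the design, and further covariates for a secondary outcome could be settled in an analysis plan that is not shown. Section D also allows methods to change. This stands: the point is an improvement, not an error. It is worth making because D.4 does list its covariates, and the better one is already in the data.

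A reader might infer that D.7's missing-at-random claim fails for H2. The text does not support that. The subject of the sentence is the general linear model, not the mixed model for control, so no explicit claim about H2 is contradicted. Multiple imputation, which D.7 leaves open, could also use baseline SBP. Bias needed dropout that depended strongly on SBP within strata and in opposite directions by arm, and the protocol gives no reason to expect that.

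A reader might also infer a material loss of power. The planned mixed model shows none that can be detected. A gain as large as 6% appears in a month-18 logistic model only if the correlation is 0.5, whereas D.3 states 0.4.

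Finally, the change has a small price. The odds ratio would then also condition on baseline SBP, and the added term assumes linearity on the logit scale. In the mixed-model simulations with dropout at random the month-18 log odds ratio hardly moved (0.630 to 0.628 untruncated, 0.613 to 0.612 truncated), but the interpretation does change.

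**Conclusion.** A valid model that leaves a small, easily recovered gain unused. At the protocol's correlation of 0.4, continuous baseline SBP is worth about 1.5 to 3% of information in the planned mixed model, with no detectable power change, and about 2 to 4% with 0 to 3 power points in a month-18 logistic model. The added robustness to dropout is a minor benefit: about 1 percentage point in the risk difference under an unfavourable mechanism, and no detectable effect when dropout depends on SBP alike in both arms (checked in the month-18 model only).

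These sizes rest on the assumptions listed with the calculations, chiefly the diabetic share and mean, the exchangeable correlation, the constant 5 mmHg effect and the assumed dropout slope. The direction of the precision gain held in every setting; its size would differ with other inputs. This is a nice-to-have change to a secondary analysis and does not affect the primary hypothesis or the sample size.

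**What to change.** In D.4, add the continuous baseline study SBP (the mean already used to assign the stratum) as a linear term, and keep diabetes status and the SBP stratum in the model. Alongside the odds ratio, report model-standardised control proportions by arm and their difference, so that the result does not depend on which covariates the odds ratio is conditional on.

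The cost is a sentence or two of protocol text. No new data, visits or patients are needed. The change should be fixed before outcome data are seen by arm.
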